8.1 Baseline Questionnaire

This will include items on: 1) past medical history, 2) current health and medication adherence, 3) lifestyle habits, and 4) attitudes towards healthcare and current mood (**Table 4; Appendix**).

TABLE 4. Components of baseline questionnaire, exclusive of questions on past medical history and lifestyle habits.

*Health-related self-efficacy⁵⁶	10-item (4-point Likert scale) survey (will be reduced to 5-items) that measures perceived ability to set-goals, cope and recover from setbacks. Results have been found to be a strong predictor of subsequent health behavior change. ⁹⁶
*PROMIS anxiety & depression^{57,58}	These domains (adult 4-item survey; all 5-point Likert scale) are of secondary interest. Prior research via a longer instrument (Profile of Mood States) did not show SCPs associated with mood changes or anxiety. ^{50,85}
*Multidimensional Health Locus of Control [MHLC]⁵⁹	18-item survey (6-point Likert scale) will classify participants with regards to their attitudes towards healthcare screening into “worried”, “collaborative” and “self-controlling” typologies, which have been associated with differential likelihoods of obtaining recommended screening in retrospective CCSS analyses. ⁷⁸
*Medication Adherence Scale (MMAS-4)⁶⁰	Well-established 4-item (0=high, 1-2=medium, 3-4=low adherence) instrument initially used to study hypertension, but since validated for other diseases. ¹⁰⁰ Will be administered separately for blood pressure, lipid, and diabetes medications. Secondary analyses will examine adherence by medication burden.

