13.3 Aim 3 Analytic Plan

Hypotheses: 1) at baseline, underdiagnosis & undertreatment are associated with lower knowledge, self-efficacy, and medication adherence (if applicable), as well as a “self-controlling” health attitude among survivors; 2) at 1-year follow-up, compared with the control arm, the intervention arm will be associated with improved knowledge, self-efficacy, and adherence rates among survivors, and improved knowledge and self-efficacy among healthcare providers.

Baseline survivor-specific factors: Using data from all Aim 1 participants, determine whether those underdiagnosed and undertreated at the time of the 1st home visit have lower knowledge (i.e., less accurate recall of prior anthracycline or chest radiotherapy exposures [chi-square test]) and lower health-related self-efficacy [t-test or Wilcoxon rank-sum] compared with those not affected. Similarly, among those who report medications for the CV risk factors of interest, determine whether those undertreated have lower medication adherence (i.e., lower mean MMAS-4 scores [t-test or Wilcoxon

rank-sum]) vs. those not undertreated. Finally, determine if different health-related behavioral attitudes (“worried”, “collaborative” and “self-controlling”)⁶⁹ are associated with differential rates of underdiagnosis and undertreatment [chi-square test]. *A priori*, we hypothesize that the proportion undertreated will be greatest among “self-controlling” survivors vs. “collaborative” and “worried” (least undertreated) survivors. In subanalyses, we will analyze underdiagnosed participants (i.e., newly diagnosed per 1st home visit) separately from those undertreated (i.e., existing diagnosis but not meeting standard therapeutic goals) relative to the referent group (those without any abnormal CV risk factor). We also will use a combined logistic regression model to determine if knowledge, medication adherence, and health-related behavioral attitudes remain associated with underdiagnosis and undertreatment (combined and separately) after multivariate adjustment. Exploratory covariates are similar as before, and include sex, current age, insurance status, healthcare utilization, self-perceived CV risk, and family history of CV disease.

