Post-intervention analysis: Among Aim 2 participants (and their designated healthcare provider), we will examine the differences between intervention and control groups following the 2nd home visit with respect to 1) survivor knowledge [chi-square test], 2) survivor self-efficacy [t-test or Wilcoxon rank-sum], 3) survivor-reported medication adherence [t-test or Wilcoxon rank-sum], and 4) provider-reported knowledge and self-efficacy [chi-square tests] related to the care of childhood cancer survivors. All analyses will be intent-to-treat and include all survivors and providers with available end points. Subanalyses can stratify these outcomes by initial underdiagnosis vs. undertreatment status. *We also will analyze practice changes over the 1-year intervention period using clinical records.* This includes comparing [chi-square test] whether documentation rates differ across study arms of: 1) any CV-related screening, 2) CV-related interventions [both lifestyle and drug prescriptions], and 3) treatment intensity (**Table 7** earlier). If any survivors share the same healthcare provider, we will apply bootstrap methods to account for the effects of clustering. In secondary analyses, we will determine, via logistic regression adjusting for randomization status, whether providers of survivors who remain undertreated have lower self-reported knowledge and self-efficacy related to the care of childhood cancer survivors vs. providers of survivors no longer undertreated.

Sample size: For covariates assessed at baseline in Aim 3, we will be able to detect differences $\geq 5\%$, RRs $\leq 0.8 / \geq 1.2$, and $\geq 20\%$ of 1 standard deviation (**Table 10**). Among randomized participants (240/arm) and subanalyses (e.g., analyzing undertreatment, underdiagnosis separately: $\sim 75-150$ /arm), detectable differences will be less.

Covariate frequency	Baseline* N=320:480	Post-intervention & subanalyses		
		240:240	150:150	75:75
10% (e.g., primary care provider self-efficacy towards childhood cancer survivorship care ^{27,28})	5%/17% RR 0.5/1.7	3%/20% RR 0.3/2.0	2%/22% RR 0.2/2.2	- /28% RR -/2.8
25% (e.g., MHLC self-controlling or worried typologies ⁶⁹ ; survivor anthracycline self-knowledge ⁷⁰)	17%/34% RR 0.7/1.4	15%/37% RR 0.6/1.5	12%/40% RR 0.5/1.6	8%/47% RR 0.3/1.9

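### Section 13.3 equates lower medication adherence with a lower MMAS-4 score, the reverse of the Table 4 key, and Table 10's baseline group sizes do not fit the MMAS-4 comparison

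*Combined protocol and SAP*

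**What the plan says.** Table 4 in Section 8.1 describes MMAS-4 as a "Well-established 4-item (0=high, 1-2=medium, 3-4=low adherence) instrument", so the score rises as adherence worsens. On its use, Table 4 adds: "Will be administered separately for blood pressure, lipid, and diabetes medications".

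The first Aim 3 hypothesis in Section 13.3 is that "underdiagnosis & undertreatment are associated with lower knowledge, self-efficacy, and medication adherence (if applicable"). The analysis paragraph then restricts the adherence comparison to a subset, "among those who report medications for the CV risk factors of interest", and asks it to "determine whether those undertreated have lower medication adherence (i.e., lower mean MMAS-4 scores", by t-test or Wilcoxon test. The comparator is survivors who are not undertreated. The same paragraph plans a "combined logistic regression model to determine if knowledge, medication adherence, and health-related behavioral attitudes remain associated with underdiagnosis and undertreatment".

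The sample size text in Section 13.3 opens with "For covariates assessed at baseline in Aim 3, we will be able to detect differences" and includes 20% of 1 SD, with no exception for adherence. In Table 10 the standard-deviation row names MMAS-4 and survivor self-efficacy as examples. It gives 20%, 26%, 33% and 46% of 1 SD for 320:480, 240:240, 150:150 and 75:75. The 60% row lists high medication adherence under the same baseline split of 320:480.

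**The concern.** The parenthetical in Section 13.3 is the only place where the baseline adherence comparison is turned into a rule about the score, and its sign contradicts the scoring key. An analyst who follows it literally would read a lower mean in the undertreated group as poorer adherence, when under Table 4 it is better adherence. A finding against the hypothesis could then be reported as support for it. The 1-year adherence comparison gives no score direction, so it would inherit whichever coding is chosen.

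Separately, Table 10 appears to give the MMAS-4 comparison a sample and a split that it does not have. If so, the stated baseline sensitivity for adherence is too optimistic, and a null result could be over-interpreted.

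**Working it through.** **Direction.** Under Table 4, lower adherence means a higher score. Section 13.3 says lower adherence means a lower mean score. Both can hold only if the score is reversed to 4 − x, and no section says so. Reversal changes the sign of the difference and nothing else. On simulated 0-4 scores, t was 4.42 on x and −4.42 on 4 − x with the same two-sided p-value, and the Wilcoxon p-value was also identical. The exposure is therefore in coding and interpretation, not in the test.

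**Table 10: reproducing the plan's figures.** I assume 80% power and two-sided alpha 0.05. These are in line with Table 9 and the Aim 2 sample size text; Table 10 shows no such line. The detectable difference in SD units is (1.96 + 0.84) × √(1/n₁ + 1/n₂) = 2.80 × √(1/n₁ + 1/n₂).

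| Groups | Computed | Table 10 |
|---|---|---|
| 320:480 | 0.202 | 20% |
| 240:240 | 0.256 | 26% |
| 150:150 | 0.324 | 33% |
| 75:75 | 0.458 | 46% |

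The arithmetic in Table 10 is sound; the question is which groups it applies to.

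**Where 320:480 comes from.** Section 13.1 expects 60% of 800 to have an abnormal finding: 0.60 × 800 = 480, leaving 320. That is no abnormality versus any abnormality. It fits self-efficacy, which Section 13.3 compares with unaffected survivors across all Aim 1 participants. It does not fit MMAS-4.

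**Group sizes for MMAS-4.** Section 13.1 expects 40% of those with abnormalities to be undertreated: 0.40 × 480 = 192. This agrees with the roughly 75 per arm used for subanalyses, since 192 × 0.80 / 2 = 77 after 20% drop-out. The remainder is 800 − 192 = 608. Section 3.3.1 counts survivors managed by lifestyle alone as undertreated, so fewer than 192 may have a score.

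The documents give no share on medication. The first row below supposes that everyone has a score; the other rows use assumed shares.

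| Share with a score (undertreated / not) | Groups | Detectable SD |
|---|---|---|
| 100% / 100% | 192:608 | 0.23 |
| 100% / 50% | 192:304 | 0.26 |
| 100% / 25% | 192:152 | 0.30 |
| 75% / 25% | 144:152 | 0.33 |
| 50% / 50% | 96:304 | 0.33 |

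If fewer people take medication, the loss is larger. With only 80 to 400 medicated in total, and 30% to 60% of them undertreated, the detectable difference is about 0.28 to 0.68 SD.

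**Does this hinge on 192?** No. With an even split, the most favourable case, 0.20 SD needs 4 × 2.80² / 0.20² ≈ 785 scored participants (using the unrounded multiplier 2.8016). That is nearly all 800, whatever the number undertreated.

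**The 60% row.** By Fisher's exact test at 80% power with a 60% reference, 320:480 gives about 49.5%/70% (Table 10: 50%/70%). For high medication adherence this becomes about 48%/71.5% at 192:608 and about 43%/76% at an assumed 96:304.

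**The case against.** The direction error is a slip in one parenthetical. The hypothesis in words and the scoring key agree, and the two-sided p-values do not change. All of that stands and keeps the point minor, but the analysis rule is still wrong as written.

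The Table 10 point draws stronger replies.

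- **Missing footnote.** The baseline column carries an asterisk whose note is absent from the available text and may qualify the group sizes. This stands as a limit on the Table 10 point; the direction error does not depend on it.
- **Examples only.** The row lists MMAS-4 as an example beside self-efficacy, which 320:480 does fit. That is fair, but MMAS-4 is named, and the sample size text repeats 20% of 1 SD without exception.
- **Other columns.** The 26%, 33% and 46% columns span the 0.26 to 0.33 SD scenarios. They are headed for post-intervention results and subanalyses, however, and the adherence test is among the main baseline comparisons.
- **Uncertain count.** The 192 could rise: the pilot behind it had only 52 high-risk survivors, the blood-pressure threshold has since been tightened, and Section 13.2 plans oversampling of rarer conditions. So 0.23 SD is not a strict bound, but the 785 calculation does not use that count.
- **Scope.** The 240:240 column likewise assumes that every randomized survivor has a score. That is correct, and it means the sample size point reaches beyond the baseline column.

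**Conclusion.** The concern holds and is minor. The direction stated in Section 13.3 contradicts Table 4, and nothing in the documents reconciles them. The risk is a coding or reporting error in the Aim 3 adherence analysis, not a changed p-value.

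The Table 10 point also holds, subject to the unseen footnote. The 20% of 1 SD is correctly computed for 320:480 but is not attainable for a comparison limited to medication users unless nearly all 800 take a relevant drug. On the plan's own rates the figure is 0.23 SD with universal medication use, so that gap is small; anything larger rests on assumed medication use. The Aim 2 primary comparison is unaffected.

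**What to change.** 1. In Section 13.3, change the parenthetical to higher mean MMAS-4 scores, or state that scores are reverse-coded. Use the same coding at 1 year; the post-intervention wording itself needs no correction.
2. Give MMAS-4 its own baseline row in Table 10, based on the expected numbers of undertreated and not-undertreated survivors with a score. Present high medication adherence on the same basis, and check whether the 240:240 entry needs the same adjustment.
3. As clarifications, state which of the three drug-class scores is analysed, for example the one matching the undertreated condition. Also state how survivors on no relevant medication enter the combined logistic model. One option is to model knowledge and attitudes in all Aim 1 participants without adherence, and add adherence in an undertreatment model among medication users.

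The cost is one phrase, one table row with a check of the neighbouring entry, and two sentences. No new data are needed.

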Among survivors found to be underdiagnosed or undertreated (Aim 1), in a randomized controlled design, compare changes in blood pressure, lipid, and blood glucose values from baseline to 1-year between those receiving the intervention (providing clinical results and survivorship care plans [SCPs] to participants and their healthcare providers, supplemented by clinician-led remote counseling sessions with participants to review SCP contents and teach CV risk factor self-management strategies) vs. control (providing clinical results without SCP to participants and their healthcare providers; with delayed access to the intervention).

- *Hypothesis: At the 1-year follow-up home visit, survivors randomized to the intervention arm will have a lower probability of having an undertreated CV risk factor compared with survivors in the control arm.*

3.1.3 Primary Aim 3

Determine barriers among (Aim 2) survivors (at baseline and 1-year: knowledge of

past cancer treatment, self-efficacy, health-related attitudes, medication adherence) and their primary healthcare providers (at 1-year only: knowledge and self-efficacy towards childhood cancer survivorship care) that contribute to undertreatment of hypertension, dyslipidemia, and diabetes.

- *Hypothesis 1: At baseline, underdiagnosis and undertreatment will be associated with lower knowledge, self-efficacy, and medication adherence, as well as a “self-controlling” health attitude among survivors.*
- *Hypothesis 2: At 1-year follow-up, intervention-arm participants will report improved knowledge, self-efficacy, and medication adherence vs. controls; healthcare providers who received the SCP will report improved knowledge and self-efficacy towards CV risk and survivorship care vs. providers of controls.*

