- **Diabetes:** American Diabetes Association classifies fasting blood glucose 100-125 mg/dL or HbA1c 5.7-6.4% as suggestive of impaired glucose tolerance (pre-diabetes). Similar to dyslipidemia, as fasting blood draws are not as commonly done in most primary care settings now for initial screening, for non-fasting (<8 hours) samples, blood glucose 140-199 mg/dL will be classified as suggestive of pre-diabetes if HbA1c was <5.7%. *Lifestyle intervention* is recommended (metformin prevention considered for select high risk populations).⁵⁴ Diabetes requires fasting blood glucose ≥ 126 mg/dL or HbA1c $\geq 6.5\%$. If not-fasting, random blood glucose ≥ 200 mg/dL would be concerning for diabetes if HbA1c was $<6.5\%$. In addition to lifestyle modifications, *metformin* is typically started with additional agents as indicated. We will ascertain the prevalence of pre-diabetes and diabetes; both may be eligible for Aim 2.

Undertreatment defined for each as:

- While any participant who was previously undiagnosed is also technically undertreated, we will reserve this definition to those who previously or currently reported to CCSS as being diagnosed with hypertension, dyslipidemia, or diabetes (either managed by lifestyle modifications or medication therapy), if their home-sampled value falls outside the recommended therapeutic range: blood pressure $\geq 130/80$ mmHg, LDL ≥ 160 mg/dL, triglyceride ≥ 150 mg/dL (if fasting <10 hours: ≥ 200 mg/dL), or HbA1c $\geq 7.0\%$ (different than the HbA1c diabetes diagnosis threshold⁶⁵).

3.3.2 **Primary Aim 2 Endpoint:** Probability of intervention subjects having an undertreated CV condition compared with the control group at 1-year follow-up.

3.3.3 **Primary Aim 3 Endpoint:** Barriers among survivors and their primary healthcare providers that contribute to undertreatment of hypertension, dyslipidemia, and diabetes.

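### The baseline knowledge and self-efficacy comparisons in Aim 3 use a referent that pools survivors with no condition and survivors diagnosed and at goal, so they cannot by themselves identify barriers to treatment

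*Combined protocol and SAP*

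**What the plan says.** Section 3.1.3 states the aim as finding barriers among Aim 2 survivors and their providers "that contribute to undertreatment of hypertension, dyslipidemia, and diabetes". Section 3.3.1 limits who can be undertreated: "we will reserve this definition to those who previously or currently reported to CCSS as being diagnosed" with one of the three conditions and whose home-visit value is out of range.

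The baseline analysis in section 13.3 draws on a wider population: "Using data from all Aim 1 participants, determine whether those underdiagnosed and undertreated at the time of the 1st home visit have lower knowledge". Self-efficacy is handled in the same way: "lower health-related self-efficacy [t-test or Wilcoxon rank-sum] compared with those not affected". The subanalyses, which take underdiagnosed and undertreated survivors separately, are made "relative to the referent group (those without any abnormal CV risk factor". Neither comparator requires a diagnosis. Table 10 sizes the baseline column at 320:480.

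Two analyses in the same section use a narrower comparator. Adherence is examined "among those who report medications for the CV risk factors of interest, determine whether those undertreated have lower medication adherence" relative to medicated survivors who are not undertreated. The secondary provider analysis asks whether "providers of survivors who remain undertreated have lower self-reported knowledge and self-efficacy" than providers of survivors no longer undertreated.

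**The concern.** A survivor who never had hypertension, dyslipidemia or diabetes cannot be undertreated, and has nothing to be underdiagnosed. Such a survivor carries no information on what stops a condition from being recognised or controlled. With these survivors in the referent, a difference in knowledge or self-efficacy may reflect who develops cardiometabolic disease, and yet be reported as a barrier. The reverse can also happen: a real difference between diagnosed survivors above and at goal can be diluted.

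Two related parts of section 13.3 are unclear rather than wrong. The health-attitude analysis speaks of rates and of the proportion undertreated without giving a denominator. The combined logistic model states no referent, and its listed covariates do not include an existing diagnosis.

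**Working it through.** **Inputs from the plan.** 800 survivors in Aim 1, 60% abnormal: 480 affected, 320 not (sections 3.1.1 and 3.4). Of the 480, 40% undertreated = 192 and 80% newly diagnosed = 384. The two sum to 120%, so the overlap is 20% = 96, and 480 - 192 = 288 are newly diagnosed only. Table 10 gives 320:480 and a detectable 20% of 1 SD. Table 9 states 80% power and alpha 0.05; I assume both apply to Table 10, two-sided.

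**Not in the available text.** The share c of the 320 who are diagnosed and at goal, and how each factor varies with disease status. Both are assumed below. The planned oversampling of rarer known conditions (section 13.2) could raise c.

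**Step 1: the plan's own figure.** Detectable difference = (1.96 + 0.842) x sqrt(1/320 + 1/480) = 2.802 x 0.0722 = 0.202 SD, against the stated 20%. Power at 0.20 SD is 79%. The table reproduces, and its group sizes are all expected affected survivors against all expected unaffected survivors.

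**Step 2: what the contrast estimates.** Write U, C and N for the mean factor level in undertreated, diagnosed-at-goal and never-diagnosed survivors. The referent mean is cC + (1-c)N, so

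U - referent = c(U - C) + (1-c)(U - N).

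The barrier to treatment is U - C, and it enters with weight c only. The rest compares undertreated survivors with survivors who have nothing to treat. This holds whatever c is. Mixing disappears only if c = 1 or if the factor is unrelated to disease status.

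**Step 3: illustration with no barrier.** Assume poor recall in 40% of all diagnosed survivors, at goal or not, and in 25% of the never-diagnosed (normal approximation). In the last two columns the 288 newly-diagnosed-only survivors also have 25%, so the affected rate is (192 x 40% + 288 x 25%)/480 = 31%.

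| c | Referent rate | 192:320 difference | Chance significant | 480:320 difference | Chance significant |
|---|---|---|---|---|---|
| 10% | 26.5% | 13.5 points | 89% | 4.5 points | 28% |
| 25% | 28.75% | 11.25 points | 74% | 2.25 points | 10% |
| 40% | 31.0% | 9.0 points | 55% | 0 | 5% |

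If the assumed gap is 5 points (40% v 35%), the 192:320 chance falls to 10-18%. If instead all 480 affected survivors differ from condition-free survivors by 0.20 SD, with no barrier, the 480:320 contrast expects (1-c) x 0.20 = 0.18, 0.15 and 0.10 SD at c = 10, 25 and 50%. It is then significant in 70, 55 and 28% of trials.

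**Step 4: illustration with a real barrier.** Assume 40% poor recall in undertreated survivors, 25% in those at goal, and 40% in the never-diagnosed. The 192:320 contrast expects c x 15 = 1.5, 3.75 and 6.0 points at c = 10, 25 and 40%, with power 6, 14 and 28%. Restricted to diagnosed survivors, 192 v 32, 80 and 128, power for 15 points is 35, 66 and 80%, pooled over conditions.

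**Step 5: precision of the at-risk contrast.** 2.802 x sqrt(1/192 + 1/n):

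| c | n at goal | Detectable difference | Power at 0.20 SD |
|---|---|---|---|
| 10% | 32 | 0.54 SD | 18% |
| 20% | 64 | 0.40 SD | 28% |
| 30% | 96 | 0.35 SD | 36% |
| 40% | 128 | 0.32 SD | 42% |
| 50% | 160 | 0.30 SD | 46% |

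Against all 320, the 192 undertreated would give 0.26 SD.

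**The case against.** Hypothesis 1 claims only that underdiagnosis and undertreatment are associated with these factors, and the planned contrast does test an association. That stands as far as it goes. But sections 3.1.3 and 3.3.3 call the factors barriers that contribute to undertreatment, and the contrast cannot carry that reading alone.

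A reader might take the 55-89% in step 3 as the false-signal rate of the main analysis. It is not. Those figures belong to the 192:320 subanalysis, under an assumed 15-point gap with no basis in the documents. The main 480:320 contrast gives 5-28% under one assumption about newly diagnosed survivors and 28-70% under another.

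A reader might also infer that the logistic model repeats the same contrast. The plan does not say so. The model includes medication adherence, which is undefined for unmedicated survivors, so it may in practice be confined to survivors close to the at-risk set. The covariate list is also described as exploratory. The fault there is missing specification.

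The at-risk comparison has limits of its own. Conditioning on diagnosis, which hypothesis 1 itself links to the same factors, can introduce selection. In the unaware v aware comparison, the aware group includes undertreated survivors, so a factor common to both failures partly cancels. Condition-specific versions would be weak. Section 2.2 puts individual undertreated conditions at 5-20%, or 40-160 survivors if the denominator is 800; with 40 v 32-128, power for 15 points is 26-45%. These points argue for adding the comparison, pooled over conditions, and for keeping the planned one.

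**Conclusion.** The point holds for the baseline knowledge and self-efficacy comparisons under hypothesis 1, and for the subanalyses with the stated referent. They relate the factors to having abnormal values, and do not separate having a condition from failing to have it diagnosed or treated. This follows from the definition in section 3.3.1, the comparators in section 13.3 and the 320:480 sizing, and needs no assumption about c.

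The size of any distortion does rest on assumptions, so the percentages above are illustrations only. That most of the 320 have no condition is plausible but cannot be checked, because the contents of Table 2 and Figure 3 are not shown in the available text.

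A reader might infer that Aim 3 as a whole is undermined. The documents do not support that. Adherence is already restricted to survivors reporting medication, the provider analysis compares remaining with resolved undertreatment, and the hypothesis 2 comparisons are between randomized arms. Aim 2 is untouched.

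**What to change.** In section 13.3, for knowledge, self-efficacy and health attitude:

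- Add, as the barrier analysis for undertreatment, a comparison among survivors reporting a diagnosis of a target condition: above goal v at goal at the 1st home visit. Pool over conditions, with adjustment for condition and for within-person correlation.
- Add, for underdiagnosis, a comparison among survivors who have the condition (reported or measured): unaware v aware.
- State the same at-risk sets for the logistic model, and give the denominator for the health-attitude rates.
- Keep the comparison with all unaffected survivors, labelled as a description of who has abnormal values.
- Treat condition-specific contrasts as exploratory.
- Reconcile the population in section 3.1.3 (Aim 2 survivors) with that in section 13.3 (all Aim 1 participants).

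No new data are needed: reported diagnoses and first-visit values are already collected on Aim 1 participants. The costs are a smaller referent, more tests, and a further entry in Table 10 for the at-risk contrast, about 0.54-0.30 SD for an assumed 32-160 survivors at goal.

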13.0 STATISTICAL CONSIDERATIONS

13.1 Aim 1 Analytic Plan

Hypothesis: Approximately 60% of participants will have an abnormal CV risk-factor finding that meets clinical intervention thresholds, and among those with abnormalities, 40% will be undertreated and 80% newly diagnosed.

Primary analyses: We will calculate the prevalence of hypertension, dyslipidemia, and diabetes by self-report and by physiologic measurement. We will then calculate the proportions (with exact 95% confidence intervals) of participants who may be underdiagnosed as well as the proportions undertreated (like **Figure 3**). We will calculate the prevalence of directly measured pre-diabetes separately. **Secondary analyses:** We will examine whether rates differ by: sex; current age; time since cancer diagnosis; obese ($BMI \geq 30 \text{ kg/m}^2$) vs. not; health insurance vs. not; recent history of being seen in a dedicated long-term follow-up clinic for survivors vs. not; and lifestyle factors (smoking, low fruit/vegetable intake, low physical activity).

Sample size considerations: Based on prevalence estimates from CCSS surveys and our pilot (**Table 2, Figure 3**), we expect ~60% of high CV risk participants ($n \sim 480$) to have an abnormal CV risk factor measurement; prevalence of individual risk factors ranging 20-40% (less when stratified by underdiagnosis/undertreatment status). With an overall sample $n=800$, we expect reasonable precision for our primary prevalence estimates (**Table 9**). Power to detect differences <10% in secondary analyses may be more limited.

TABLE 9. Estimated power for Aim 1 analyses.		
Prevalence \pm 95% CI	Minimum detectable proportions*	
N=800	N=320:480	N=200:200
5% \pm 1.5%	5% vs. 1/11%	5% vs. 0/14%
20% \pm 2.8%	20% vs. 12/29%	20% vs. 10/33%
50% \pm 3.5%	50% vs. 40/60%	50% vs. 36/64%

*2-sample Fisher's exact test, 80% power, $\alpha=0.05$.

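### The Aim 3 combined logistic model uses medication adherence to explain underdiagnosis as well as undertreatment, with no restriction to survivors who take a CV drug and so have an adherence score

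*Combined protocol and SAP*

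**What the plan says.** Section 13.3 handles adherence at baseline in two steps.

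- Unadjusted: "among those who report medications for the CV risk factors of interest, determine whether those undertreated have lower medication adherence". This is a comparison within medication users, of undertreated against not undertreated. No unadjusted test of adherence against underdiagnosis is planned.
- Adjusted: a "combined logistic regression model to determine if knowledge, medication adherence, and health-related behavioral attitudes remain associated with underdiagnosis and undertreatment". The two outcomes are to be modelled both together and apart. No analysis population, no category for survivors on no drug and no rule for scores that are missing by design is given.

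The hypothesis at the head of section 13.3 reads "underdiagnosis & undertreatment are associated with lower knowledge, self-efficacy, and medication adherence (if applicable", with that last qualifier. The same hypothesis in section 3.1.3 has no qualifier: "At baseline, underdiagnosis and undertreatment will be associated with lower knowledge, self-efficacy, and medication adherence".

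Table 4 in section 8.1 says of MMAS-4: "Will be administered separately for blood pressure, lipid, and diabetes medications". A survivor may therefore have none, one, two or three scores, and no rule turns them into one variable.

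Section 3.1 defines underdiagnosis as having the risk factor without knowing it. Section 3.3.1 allows an undertreated survivor to be managed by lifestyle alone. Table 10 lists MMAS-4 in the row with a detectable difference of 20% of 1 SD at 320:480.

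**The concern.** The model pairs a predictor with an outcome for which it is not defined. A survivor unaware of a condition takes no drug for it and cannot adhere to one. Any score such a survivor has belongs to a different, known condition.

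Logistic regression software by default keeps only rows with every predictor present. That would remove three kinds of survivor: underdiagnosed survivors on no CV drug, referents on no CV drug, and undertreated survivors managed by lifestyle alone. The referents left would be medicated and controlled, not simply free of abnormal values. Knowledge and attitudes sit in the same model, so their adjusted coefficients would come from the same selected subset, although both are collected from everyone.

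This is the only adjusted analysis planned for the baseline hypothesis. With the population and coding left open, the analyst must choose after seeing the data between dropping non-users, giving them a code, or removing the term. These choices can give different answers.

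**Working it through.** **1. Reproduce the plan's adherence figure.** Inputs: 320:480 and the other group sizes (Table 10); 80% power and α = 0.05 (footnote to Table 9, taken as two-sided and carried to Table 10). The minimum detectable difference (MDD) in SD units is (z₀.₉₇₅ + z₀.₈₀) × √(1/n₁ + 1/n₂), with 1.960 + 0.842 = 2.802.

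- 320:480 gives 0.202 (stated 20%)
- 240:240 gives 0.256 (stated 26%)
- 150:150 gives 0.324 (stated 33%)
- 75:75 gives 0.458 (stated 46%)

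The table reproduces. The baseline entry for MMAS-4 therefore assumes a score for all 320 + 480 = 800 participants.

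**2. Break down the affected survivors on the plan's rates.** Section 13.1 expects 60% of 800 = 480 abnormal and, "among those with abnormalities, 40% will be undertreated and 80% newly diagnosed".

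- Undertreated: 0.40 × 480 = 192
- Underdiagnosed: 0.80 × 480 = 384
- Both: 192 + 384 − 480 = 96, or 20% of 480, which agrees with the 20% overlap in the pilot (section 2.2)
- Underdiagnosed only: 384 − 96 = 288, and 288/384 = 75%
- Referents: 800 − 480 = 320

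The 288 have a score only through a different condition that is known, medicated and controlled. In the pilot, reading the 23% as part of the 37% with an abnormal value, 23/37 = 62% of those with an abnormal value reported none of the three conditions. That figure is for the whole pilot sample and uses higher cut-points, so it is supporting evidence only.

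**3. Restrict to survivors with a score.** The readable text gives no drug-use shares. Assume m = share of the 192 undertreated on a CV drug (also applied to the 96 with both), u = share of the 288 on a drug for another condition, and r = share of the 320 referents on a CV drug. Then affected scored = 192m + 288u, underdiagnosed scored = 96m + 288u, and referents scored = 320r.

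| m, u, r (assumed) | Scored of 800 | Underdiagnosed scored of 384 | MDD, affected vs referents | MDD, underdiagnosed vs referents |
|---|---|---|---|---|
| 0.5, 0, 0.1 | 96 + 32 = 128 (16%) | 48 (12%) | 0.57 SD | 0.64 SD |
| 0.75, 0.25, 0.2 | 216 + 64 = 280 (35%) | 144 (38%) | 0.40 SD | 0.42 SD |
| 1, 0.4, 0.5 | 307 + 160 = 467 (58%) | 211 (55%) | 0.27 SD | 0.29 SD |

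Power for a true difference of 0.20 SD, affected against referents, is 16%, 29% and 54%.

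The planned unadjusted test splits the same scored survivors by undertreatment: 192m against 288u + 320r. This gives 96:32, 144:136 and 192:275, with MDDs of 0.57, 0.33 and 0.26 SD. The conclusion is the same: each exceeds 0.20.

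**4. When are fewer than half of the underdiagnosed scored?** When 96m + 288u < 192, that is u < (192 − 96m)/288. The limit is 50% for m = 0.5, 42% for m = 0.75 and 33% for m = 1.

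**5. Compare predictors with the hypothesis.** Self-efficacy is in the hypothesis and has its own unadjusted test. It appears neither among the combined model's named predictors nor among its exploratory covariates.

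**The case against.** The strongest reply is that the plan already knows adherence applies only to some. The hypothesis in section 13.3 carries its qualifier, the unadjusted test is limited to those "among those who report medications for the CV risk factors of interest", and asking whether factors remain associated refers back to those tests. On this reading the gap is an unstated population, not an intention to score non-users. That is fair as to intent. It does not settle the model, because carrying the restriction forward would confine the knowledge and attitude terms to medication users too, and no earlier test links adherence to underdiagnosis.

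A reader might go further and infer that the model would lose most underdiagnosed survivors and most referents. The documents do not support that. The counts in step 2 are by diagnosis, not by drug use. In the highest scenario 55% of the underdiagnosed have a score, and nothing readable gives a share for referents. The oversampling of rarer known conditions in section 13.2 could also raise the medicated share.

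The plan does not state complete-case fitting; that is an inference about usual practice. A category for survivors on no CV drug would keep everyone. But being on no drug partly follows from being undiagnosed or having no condition, so for underdiagnosis it would reflect diagnosis status rather than behaviour.

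Table 10 is a general grid whose smaller columns reach 33% and 46% of 1 SD, and the note marked on its baseline column is not visible in the available text. Even so, MMAS-4 is named in the row whose 320:480 entry needs all 800 scored.

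The unadjusted knowledge, self-efficacy and attitude tests are unaffected. The synopsis lists Aim 3 as secondary, although section 3.1.3 heads it as primary.

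**Conclusion.** The point holds as a fault in model specification. The combined model enters adherence for underdiagnosis, where it can only describe a drug for another condition, and drops the restriction that the plan itself applies one step earlier. If fitted on available data, its knowledge and attitude coefficients describe a selected medicated group.

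On the plan's rates, 75% of the underdiagnosed (288 of 384) depend on treatment for another, controlled condition to have any score. How many would be lost is unknown. The MDD range of 0.57 to 0.27 SD, against the stated 0.20, rests on assumed drug-use shares and on an unadjusted two-group comparison. It shows direction and rough size, not a forecast.

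The randomized Aim 2 comparison is not touched. The change should be made before the baseline analysis is run.

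**What to change.** 1. Fit the adjusted model in all Aim 1 participants without adherence. Include knowledge, self-efficacy, attitude typology and the covariates already listed, for underdiagnosis and undertreatment, combined and separately.
2. Fit a second model only among survivors taking a CV drug, with undertreatment as the outcome and the MMAS-4 score for the matching drug class added. If there is one row per condition, cluster the standard errors on survivor. If one row per survivor is preferred, state how the scores are combined. Do not interpret an adherence term for underdiagnosis.
3. In Table 10, restate the baseline MMAS-4 entry for medication users, using the drug-use shares seen in the cohort's surveys or at baseline. The 60% row, which names high adherence, needs the same change. The self-efficacy figure can stay.

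The cost is a paragraph of SAP text, one extra model and a less favourable stated detectable difference for adherence. No new data are needed.
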